PARTICIPANTS: For Aims 1, 1a, 2, 2a, two groups (n=36 each) of women will be recruited to complete this study: 1) IR, obese young women between the ages of 18 and 40 years (Controls); 2) IR, obese young women between the ages of 18 and 40 years with AE-PCOS. For Aim 3, two groups (n=16 each) of women will be recruited to complete this study: 1) IR, obese young women between the ages of 18 and 40 years (Controls); 2) IR, obese young women between the ages of 18 and 40 years with AE-PCOS. As women sign up for the study, they will complete medical histories, including the **Berlin questionnaire** (www.sleepmedicine.com) to screen for Obstructive Sleep Apnea (See Appendix 1). They will also fill out a hair growth chart. Subjects who smoke, have diabetes, sleep apnea or BP>140/90 will be excluded. Subjects will not be taking medications during the study, including any insulin sensitizing, CV medications, or hormonal contraception for at least four weeks prior to participating in these protocols. We do make exceptions for Tylenol in the event the subject has acute pain. All women (early proliferative phase in Controls) will undergo **3-hr oral glucose tolerance test (OGTT; 75 gram glucose load)** to determine IR (8). We define our subjects in both groups as having IR with AUC of glucose 140-200 mmol/L and AUC of insulin 40-90 μ U (57, 64). Sexually active participants will use barrier contraception for the duration of the study, and take pregnancy tests within 24 hours of participation. Subjects are excluded if they have lost > 5 kg of weight within the past 6 months or exercise more than three times/week. At their initial consent visit, after signing the consent form, subjects will be randomly assigned to take a GnRH antagonist with or without methyl testosterone (see “Study Design” below). They will be told immediately of the results of the randomization.

AE-PCOS subjects: Diagnosis of AE-PCOS will be based on modified NIH criteria requiring the presence of *both* **clinical hyperandrogenism** (hirsutism based on Ferriman Gallwey score of >8 and/or acne), and **biochemical hyperandrogenemia** (elevated serum total testosterone; ELISA,

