see Authentication). **Anovulation** (defined as a total of \leq 8 menses per year) and presence of **polycystic ovarian morphology** on transvaginal ultrasound as determined by a trained obstetrician/gynecologist ([name]), **obesity and IR** will be additional enrollment criteria for the AE-PCOS population. **Sex as a biological variable:** Only females will be used for these studies since AE-PCOS is a female-specific disorder.

Control subjects will be **obese, IR** women, with regular menses every 26-34 days. Subjects will be excluded if they have any symptoms of AE-PCOS subjects, including polycystic appearing ovaries (as determined by transvaginal ultrasound ([name])).

For Aim 1, 2 and 3: All subjects will be given urine collection containers to collect their overnight urine prior to visits 4,5 and 6.

For Aim 1, 2 and 3: All subjects will self administer Antagon injections for a total of 10 days. Subjects may be kept on Antagon for as long as 18 days if there is a challenge with experiment scheduling. Subjects will also ingest a testosterone pill for seven days. Subjects may also be kept on testosterone for up to 11 days with regard to scheduling issues.

For Aim 5: Subjects will participate in only one baseline study (Fig 7). We will recruit black and white women to participate in this study with AE-PCOS.

EXPERIMENTAL PROTOCOLS:

Aims 1 & 2. Study design (Fig 7) and Hormone administration (Fig 8): IR subjects with and without AE-PCOS will be randomly (MiniTab, © cleverbridge, Inc.) divided into two **Protocol** groups (4 groups total, n=18 each) to be tested 3 times each: **Protocol 1:** prior to GnRH antagonist (Day 1); GnRH antagonist (250 μ g/day in 0.5 ml normal saline, Days 3 and 10). **Protocol 2:** prior to GnRH antagonist (Day 1), GnRH antagonist alone (Day 3), GnRH antagonist + methyltestosterone (Day 10). In both Protocols, Day 1 in Controls occurs in the proliferative phase of the menstrual cycle (days 1-7, low hormone phase); GnRH suppression begins on days 26-28 of that cycle. Non-cycling women with AE-PCOS begin testing at their convenience.

*Women may take the Antagon pills for as long as 18 days. We allow this flexibility because of challenges with scheduling subjects. There is no increase in risk, and we do everything possible to avoid the rare instance where taking this drug needs to be extended. If the drug is extended, "day 10" procedures occur on the final day of "GnRH antagonist + methyltestosterone" administration.

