Visit 5: GnRH): **Baroreflex and RAS testing**

Visit 6: GnRH): **Baroreflex and RAS testing**

Visit 1: Screening, informed consent, orientation:

We will describe the study in detail. Subjects will fill out a medical history form (including medications) so we can make sure it is safe for the participant to be in this study. They will have a pregnancy test at no cost and if eligible for the study and decide to participate, we will teach them how to give a self-injection of Antagon, a drug that will be used in this study. We will also orient the participant to where the research studies will be done and demonstrate the equipment and procedures that will be used for the study.

Visit 2. Transvaginal ultrasound. The subjects will undergo evaluation using transvaginal ultrasound. We will perform transvaginal ultrasound using a linear probe on a Phillips 3-D ultrasound on all subjects. There are no known risks associated with this procedure. The procedure is painless and will require approximately twenty minutes to perform. The ultrasound examination will be performed in the Yale Center for Reproductive Medicine by a gynecologist on the staff of the Yale New Haven Hospital and who is accredited by the American Institute for Ultrasound in Medicine. The ultrasound will be a focused exam looking only at the ovaries. With the subject's permission, any incidental pathology noted at the time of the exam will be sent to the subject's private gynecologist for possible further evaluation. All follicles and/or cystic structures are measured. Ovarian volume is calculated as the measure of a prolate ellipsoid. Ovarian morphology is determined by the methods described in the literature for identifying polycystic ovaries in women with PCOS (3, 4).

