Visit 3. Oral glucose tolerance test. Subjects will undergo an **OGTT at The John B. Pierce Laboratory** to quantify glucose tolerance and insulin resistance. These tests are done in the early proliferative phase of the menstrual cycle in cycling women. A standard (3 hour) OGTT will be conducted to determine glucose tolerance in all subjects within 2 weeks of the start of the study. One hour will be added for postural acclimation and insertion of the IV for a total of a 4 hour visit. Blood samples for serum concentration of glucose and insulin will be drawn at baseline prior to ingestion of a 75g glucose beverage (Glucose Drink; Azer Scientific, Morgantown, PA) and at every 30-minute time point following drinking for three hours. A total of 45ml (3 tablespoons) will be drawn.

Visits 4-6 (Visits 5 and 6 are identical to Visit 4):

Protocols 1A-B: Autonomic function: Baroreflex testing (Fig 9). We will examine **autonomic function** in our human subjects at **rest** (cardiovagal), during **Valsalva maneuver** (sympathetic), during the **modified Oxford protocol** (sympathetic, **Fig 9**) (20, 23, 33, 42) and with **integrated baroreflex** response during **LBNP** (23, 103). Our primary measure of SNSA is peripheral nerve activity, as measured by **muscle sympathetic nerve activity (MSNA)**. We will also determine HR, BP (EKG and beat-to-beat), and a catheter will be inserted into a forearm vein for blood sampling. Following the instrumentation period, resting HR, pulse (or R-R) interval (PI), BP, and MSNA will be recorded for 10 minutes, and a blood sample drawn for analysis of S_[E₂], progesterone (S_[P₄]), sex hormone binding globulin, (P_[SHBG]), albumin, free (P_[free]) and bound (P_[T]) testosterone, S_[ALD], serum angiotensin converting enzyme (S_[ACE]), angiotensinogen (S_[ANG]), renin, (P_[Renin]), PRA, P_[ANG II], norepinephrine (P_[NE]), epinephrine (P_[EPI]), electrolytes, creatinine (Cr) and osmolality (P_[Osm]). After the first blood sample and a **30-min rest phase**, subjects will begin a seven-minute period of **rest with paced breathing** (12 breaths per minute) while HR, BP and MSNA are measured (**Fig 9**).

[figure not shown]

Figure 9. Modified

The subjects will synchronize breathing to a metronome set to a cadence of ~12 breaths per minute (0.2 Hz). Following baseline measurements, subjects will perform two **Valsalva maneuvers**. Methods are described in Procedures.

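### Women are randomised and told their arm at the consent visit, before eligibility is confirmed and before two test days that are identical in both arms

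*Combined protocol and SAP*

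**What the plan says.** Section V.3, Participants, fixes the time of allocation: "At their initial consent visit, after signing the consent form, subjects will be randomly assigned to take a GnRH antagonist" with or without methyltestosterone. The next sentence adds: "They will be told immediately of the results of the randomization".

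The visit list makes consent Visit 1. The ultrasound follows: "Visit 2. Transvaginal ultrasound. The subjects will undergo evaluation using transvaginal ultrasound". The glucose tolerance test is Visit 3, where "Blood samples for serum concentration of glucose and insulin will be drawn at baseline" and at later time points. Both tests decide eligibility. Polycystic morphology is required for AE-PCOS and excludes a Control, and insulin resistance is required in both groups (Section V.3, Participants; Section V.7). AE-PCOS also requires a raised serum total testosterone.

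The description of Visit 1 does not mention randomisation. It says that "if eligible for the study and decide to participate, we will teach them how to give a self-injection of Antagon", which applies to every woman whatever her arm.

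The study design text for Aims 1 & 2, and again for Aim 3, says "IR subjects with and without AE-PCOS will be randomly" divided into two Protocols, with cells of 18 (Aims 1 & 2) or 8 (Aim 3). It gives no time point. Both Protocols test before the antagonist on Day 1 and on antagonist alone on Day 3. After Day 1, Protocol 2 runs "GnRH antagonist alone (Day 3), GnRH antagonist + methyltestosterone (Day 10"), while Protocol 1 stays on antagonist alone at Day 10.

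**The concern.** Two things can go wrong when the arm is generated and disclosed this early.

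First, some allocated women will turn out not to be eligible. They must then be dropped after randomisation or kept although ineligible. Any allocation within diagnosis would also rest on provisional status from phone screening, history and the hair chart.

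Second, a woman knows her arm through a period in which the arms are treated alike. She may withdraw at any time (Section VII.9). If she leaves because of her arm, the loss is related to allocation although no difference in treatment has yet occurred. Her Day 1 and Day 3 recordings are also made with the arm known to her. Nothing listed for Visit 1 needs the arm to be known then.

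At stake is the only randomised comparison in the study: antagonist with versus without methyltestosterone.

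**Working it through.** **The plan's nearest figure.** The plan gives no screen-failure or arm-related withdrawal rate. The only related figure is the allowance of about 20% that takes 15 evaluable women to 18 per group: 15 × 1.2 = 18 (15 / 0.8 = 18.75 would give 19). The sample size text attributes it to microneurography failure, not to screening.

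**Order of events.**

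| Step | Arm known to the woman? | Do conditions differ by arm? |
|---|---|---|
| Visit 1: consent, allocation, disclosure | from here on | no |
| Visit 2: ultrasound (eligibility) | yes | no |
| Visit 3: glucose tolerance test (eligibility) | yes | no |
| Visit 4: Day 1 test | yes | no |
| Visit 5: Day 3 test | yes | no |
| Visit 6: Day 10 test | yes | yes |

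Two eligibility visits and two of the three test visits fall after disclosure and before the arms differ.

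**Time between the Day 1 test and the antagonist start in Controls.** The documents give two test windows and two start windows.
- Cycle days 1–7 (study design text), where "GnRH suppression begins on days 26-28 of that cycle": 26 − 7 = 19 to 28 − 1 = 27 days.
- Days 8–12 (Research Design, Group 2 paragraph) with start on days 26–28: 26 − 12 = 14 to 28 − 8 = 20 days.
- Start on days 25–27 (Section V.9, GnRH antagonists): from days 1–7, 25 − 7 = 18 to 27 − 1 = 26 days; from days 8–12, 25 − 12 = 13 to 27 − 8 = 19 days.

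Across these texts the range is 13 to 27 days. Non-cycling women with AE-PCOS start testing at their convenience.

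**Screen failure (rate f assumed).** The number to allocate at Visit 1 so that n eligible women remain is n / (1 − f), rounded up. For imbalance I take a balanced list of N women, floor(N/2) in one arm, from which n eligible women remain at random (hypergeometric), and compute the chance that the arms differ by 4 or more.

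| f | Aims 1 & 2, n = 36 per diagnosis: N (found ineligible) | P(difference ≥ 4) | Aim 3, n = 16 per diagnosis: N (found ineligible) | P(difference ≥ 4) |
|---|---|---|---|---|
| 0% | 36 (0) | 0 | 16 (0) | 0 |
| 10% | 40 (4) | 0.11 | 18 (2) | 0 |
| 20% | 45 (9) | 0.28 | 20 (4) | 0.09 |
| 30% | 52 (16) | 0.37 | 23 (7) | 0.19 |

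**Cost of that imbalance.** Information relative to an equal split is 4ab / (a + b)².
- 16:20 gives 4 × 16 × 20 / 36² = 1280 / 1296 = 0.99.
- 6:10 gives 4 × 6 × 10 / 16² = 240 / 256 = 0.94.

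**Arm-related withdrawal.** If k of n women in a cell leave and differ from the rest by d SD, the cell mean moves by k × d / n. For a stable difference in level, both the Day 3 and the Day 10 means of the remaining women move by that amount, so the Day 3 to Day 10 change does not move. The change is biased only if leavers would have responded differently to methyltestosterone, or to continued antagonist, from those who stay.

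**The case against.** The best case against the point is that the study design text already speaks of insulin-resistant women with and without AE-PCOS, so allocation may in practice follow screening. That reading is possible, but the text gives no time point, the Participants text does, and Figures 7 and 8 are not available to settle it. What stands is that the two texts must be reconciled.

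Four stronger readings are tempting, and the documents do not support them.

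- *A reader might infer that early allocation costs sample size or power.* Obtaining 36 eligible women at 20% screen failure means assessing about 45 whenever randomisation happens, and the plan recruits 36 per group to complete the study. Timing adds only the risk of imbalance, which costs little.
- *A reader might infer a material bias from withdrawals.* If 3 of 18 leave and differ by 1 SD (assumed), the cell mean shifts by 3 × 1 / 18 = 0.17 SD, against a standard error of √(2/18) = 0.33 SD. But the planned analysis is repeated-measures ANOVA on women tested three times, so a stable difference in level largely cancels. Nothing in the documents suggests that leavers would respond differently.
- *A reader might infer that the whole study is affected.* Suppression is tested within women, and Control versus AE-PCOS is not randomised. Both arms are handled alike through Day 3, so allocation timing does not reach those comparisons through a difference between arms.
- *A reader might infer that no diagnostic testosterone is available before allocation.* The first such sample tied to a visit is at Visit 4, but the criterion points to an Authentication section that is not in the text supplied. The timing is unconfirmed, not shown to be absent.

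Also fair: moving allocation only to the end of screening still discloses the arm before Day 1 and Day 3.

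**Conclusion.** The point holds, with limited weight. As written, the arm is assigned and disclosed before eligibility is confirmed and before two test days with identical conditions, and the documents are not consistent about when allocation occurs.

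Only the contrast with versus without methyltestosterone is exposed. The size cannot be derived from the documents and is probably small. Exclusions on ultrasound or glucose tolerance are unlikely to depend on arm. The imbalance they could cause keeps 94% to 99% of the information in the splits shown. Arm-related withdrawal matters only as far as it happens and is linked to response rather than level; it is zero if nobody leaves because of her arm. The screen-failure rates of 0% to 30% and the balanced list at Visit 1 are assumptions.

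The change is worth making because it is cheap and protects the one randomised comparison, not because a large bias has been shown.

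**What to change.** **Minimum.** State one time point for randomisation and bring the Participants, study design and Visit 1 texts into line with it. At Visit 1, obtain consent to either arm. Generate and disclose the allocation, within diagnosis, only after the ultrasound, the glucose tolerance test and the diagnostic testosterone result are available, and state when that testosterone sample is drawn. This moves one step and adds no visit or staff. If no screening sample exists at present, one draw is added. The consent wording changes, and unwillingness to take methyltestosterone must be settled at consent.

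**Preferred.** Defer allocation and disclosure until the Day 3 tests are complete, just before methyltestosterone would start. Only this closes the route through withdrawal and knowledge of the arm before the arms differ. It costs more: the compounded methyltestosterone must be ready for every woman, including the half who will not take it.

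**Either way.** Analyse the contrast with versus without methyltestosterone in the women so randomised. Report losses and removals before and after allocation separately, and by arm after allocation. Neither option masks the Day 10 tests, which remain open-label, or prevents later withdrawals.

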Preliminary Testing. Because naive volunteers may be used, all subjects are brought to the laboratory prior to the experimental days, thoroughly trained in all maneuvers and familiarized with all routines to ensure that they are as comfortable as possible on the first experimental day. Each subject is individually trained on how to do the GnRH antagonist injection, either by the PI, the Post Doc or a nurse at the Reproductive Endocrinology clinic. During the training, the subject is shown how to clean the area first with an alcohol pad, how to open the package with the syringe to avoid sticking their fingers and to maintain sterility. The subjects are taught to use either their leg or abdomen, and how to insert the needle and press down to inject the fluid. They are also taught to use pressure should there be bleeding after the injection. In addition, the subjects are all provided with detailed instructions provided by the manufacturer, alcohol pads and sterile gauze pads.

Research Design:

Group 1 (Fig 8):

- 1) prior to GnRH suppression;
- 2) during GnRH suppression (Ganirelix acetate alone, 250 µg/day in 0.5 ml normal saline, 2 days);
- 3) Ganirelix + methyltestosterone ((oral, 5.0 mg/day, 7 days (on day 10));

Group 2 (Fig 8):

- 1) prior to GnRH suppression;
- 2) during GnRH suppression (Ganirelix acetate alone, 250 µg/day in 0.5 ml normal saline, 2 days);
- 3) during GnRH suppression (Ganirelix acetate alone, 250 µg/day in 0.5 ml normal saline, 2 days) and again at 10 days; Control subjects will first be tested in the proliferative phase of the menstrual cycle (days 8-12) because estrogen status at this time is similar to non-cycling PCOS subjects.

Women with normal menstrual cycles will begin GnRH suppression on days 26-28.

Women may take the Antagon pills for as long as 18 days. We allow this flexibility because of challenges with scheduling subjects. There is no increase in risk, and we do everything possible to avoid the rare instance where taking this drug needs to be extended. If the drug is extended, "day 10" procedure occur on the final day of "GnRH antagonist + methyltestosterone" administration.

Research Protocol (Fig 8):

Visit 1: **Screening, informed consent, orientation.**

Visit 2: **Ultrasound (YMG)**

Visit 3: **Oral glucose tolerance test (OGTT).**

Visit 4: (BL): **Baroreflex and RAS testing**

Visit 5: (GnRH): **Baroreflex and RAS testing**

Visit 6: (GnRH +T): **Baroreflex and RAS testing**

OR

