GnRH antagonists (Antagon and Cetrotide) put the subjects into a temporary menopausal state, so they may experience vasomotor symptoms (i.e. “hot flashes”) during the initial period of administration. Additionally, although most women tolerate Antagon quite well, some may experience headaches, breast tenderness, transient mood changes, some temporary bloating of the abdomen and moderate irregular vaginal bleeding. In our studies, the subjects begin the Antagon/Cetrotide treatments on days 25-27 of their menstrual cycle (or ~11-12 days after ovulation) to avoid discomfort to irregular bleeding, so this has not been a reported side effect in our experience. There are no documented long-term side effects of Antagon. Subjects in our studies have reported minimal side effects from using Antagon over a period of 16 days. In one of our studies, one of 15 subjects reported occasional vasomotor symptoms during Antagon treatment. In our >10 years of using Antagon, two subjects reported transient changes in mood during Antagon treatment. The subjects reported no other adverse effects due to the Antagon or hormone administration, and the side effects did not cause any of the subjects to leave the study.

Elagolix (Aim 4) In our studies, the subjects with menstrual cycles begin the elagolix treatment on days 1-7 of their menstrual cycle (or 1-7 days after the beginning of menstruation) to avoid discomfort due to irregular bleeding, though this has not been a reported side effect. Long-term side effects of elagolix include the potential for bone loss however this risk is not relevant after short exposures (<6 months of continuous use). We have not used elagolix in our studies before, but subjects in our studies have reported minimal side effects from using Antagon over a period of 16 days. There will be at least one month between the end of taking GnRH Antagonist ganirelix acetate for the first part of this study and beginning this part to ensure washout of the ganirelix acetate. Subcutaneous injections of ganirelix acetate is associated with a mean half-life of 12.8 hours are almost completely (69, 70) Thus providing a month “washout” between finishing ganirelix acetate and elagolix, both well tolerated drugs, should cause no danger to the subjects.

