Aims 1 & 2. Subjects will receive up to \$800.00 for participating in all aspects of the study. Subjects will not be charged for any of the tests. They will be paid \$40.00 for the orientation procedure (including ultrasound), \$60 for the oral glucose tolerance test, \$150.00 for each blood pressure research study, \$15.00 for each day they are taking Antagon, and a \$100.00 finishing bonus. If they do not complete all parts of the study, they will be paid for the parts completed. Payment will be in check form following completion of the study.

Aim 3. Subjects will receive up to \$770.00 for participating in all aspects of the study. Subjects will not be charged for any of the tests. They will be paid \$40.00 for the orientation procedure (including ultrasound), \$60 for the oral glucose tolerance test, \$100.00 for each blood pressure research study, \$15.00 for each day they are taking Antagon, and a \$100.00 finishing bonus. If they do not complete all parts of the study, they will be paid for the parts completed. Payment will be in check form following completion of the study.

Aim 4. Subjects will receive up to \$200 for participating in all aspects of the study. They will be paid \$50 for each blood draw, \$10 for each day taking Elagolix, and a \$30 finishing bonus. If they do not complete all parts of the study, they will be paid for the parts completed. Payment will be in check form following completion of the study.

Aim 5. Subjects will receive up to \$350.00 for participating in all aspects of the study. Subjects will not be charged for any of the tests. They will be paid \$40.00 for the orientation procedure (including ultrasound), \$60 for the oral glucose tolerance test, \$150.00 for the blood pressure research study, and a \$100.00 finishing bonus. If they do not complete all parts of the study, they will be paid for the parts completed. Payment will be in check form following completion of the study.

3. **Costs for Participation (Economic Considerations):** Clearly describe the subject's costs associated with participation in the research, and the interventions or procedures of the study that will be provided at no cost to subjects.

There will be no costs to subjects. If transportation is required the laboratory will reimburse up to \$20. According to the rules of the Internal Revenue Service (IRS), payments that are made to the subject as a result of their participation in a study may be considered taxable income.

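### The dosing-extension note conflicts with the rest of the plan on drug form, gives the antagonist-only arm no extended test day, and allows an antagonist duration that the androgen limit rules out

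*Combined protocol and SAP*

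**What the plan says.** All places are in the combined protocol and SAP.

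- **Planned dosing** (Section V.3, Participants, paragraph for Aims 1 to 3): "All subjects will self administer Antagon injections for a total of 10 days". Testosterone is taken for seven days.
- **Maximum dosing** (same paragraph): "Subjects may be kept on Antagon for as long as 18 days if there is a challenge with experiment scheduling", and "Subjects may also be kept on testosterone for up to 11 days with regard to scheduling issues".
- **Extension note** (Section V.3, after the Aims 1 and 2 design, and again under Research Design): "Women may take the Antagon pills for as long as 18 days". The note says that this adds no risk and that extension is rare. If dosing is extended, the Day 10 "procedures occur on the final day of" combined antagonist and methyltestosterone administration.
- **Drug form elsewhere** (Section V.3, Preliminary Testing): "Each subject is individually trained on how to do the GnRH antagonist injection". Visit 1 also teaches self-injection.
- **Arms.** One arm takes the antagonist alone and is tested on Day 1, Day 3 and Day 10 (Protocol 1 in the Aims 1 and 2 design, Group 2 under Research Design). The other is tested on the antagonist alone at Day 3 and on antagonist plus methyltestosterone at Day 10.
- **Experience cited** (Section V.9, Risks): "minimal side effects from using Antagon over a period of 16 days".
- **Payment** (Section X.2): 15 dollars "for each day they are taking Antagon", with ceilings of 800 dollars for Aims 1 and 2 and 770 dollars for Aim 3.

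**The concern.** The antagonist-only arm shows what continued suppression does without added androgen, so it is the natural time control for the add-back arm at the final visit. That use needs the two arms to be tested after comparable antagonist exposure. The extension note defines the moved test by a regimen that only one arm receives. An extended woman on the antagonist alone would be tested on a day chosen locally, and an extended add-back woman on a day that may not match it. The final-visit difference between arms could then mix the androgen effect with length of suppression.

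There is also a conduct problem. Staff who follow the 18-day allowance in the add-back arm, with the Day 3 test where the plan puts it, will breach the plan's own androgen limit.

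**Working it through.** **Planned schedule.** Inputs: antagonist alone up to the Day 3 test, 7 androgen days, final test on Day 10. A 3-day lead-in gives 3 + 7 = 10 antagonist days, which reproduces the stated total. Research Design describes the lead-in as two days, which gives 2 + 7 = 9 dosing days before a Day 10 test. Both lead-ins are carried forward.

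**Do the two maxima fit with a fixed Day 3 test?** Androgen starts after the Day 3 test and runs to the final test.

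- Antagonist taken to 18 days: androgen days = 18 − lead-in, so 18 − 3 = 15 or 18 − 2 = 16. Both exceed 11.
- Androgen held to 11 days: antagonist days = lead-in + 11, so 3 + 11 = 14 or 2 + 11 = 13. Both fall short of 18.
- Both maxima used in full: 18 − 11 = 7 antagonist-alone days are needed first. The note moves only the Day 10 test and says nothing about a later androgen start or a longer lead-in.

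So the full 18 days cannot be used in the add-back arm under the other stated rules. The androgen limit does not bind the antagonist-only arm. If every limit is respected, the longest possible antagonist exposure is 13 to 14 days in one arm and 18 in the other, a gap of 4 to 5 days.

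**Extended test day by arm.** Add-back arm: the last day of combined dosing, which exists. Antagonist-only arm: the same phrase, which describes no day in that regimen. The text gives no other rule. Figures 7 and 8, which show the design and hormone schedule, were not available, so this holds for the prose only.

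**Cited experience.** 18 − 16 = 2 days beyond the duration mentioned under Risks.

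**Durations implied by the payment ceilings.** Each total is 40 (orientation) + 60 (glucose test) + three test visits + 15 per Antagon day + 100 (bonus).

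- Aims 1 and 2: 40 + 60 + 3 × 150 + 100 = 650; (800 − 650) / 15 = 10 days. At 18 days the total is 650 + 15 × 18 = 920 dollars, 120 above the ceiling.
- Aim 3: 40 + 60 + 3 × 100 + 100 = 500; (770 − 500) / 15 = 18 days.

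The same extension allowance covers Aims 1 to 3, yet the two ceilings assume different durations.

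**Scale.** Each arm within a diagnosis group has 18 women in Aims 1 and 2 and 8 in Aim 3, so one extended woman is 1/18 = 5.6% or 1/8 = 12.5% of a cell. The number of extensions is not given.

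**The case against.** Several stronger readings are tempting, and the documents do not support them.

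- A reader might infer that the plan contradicts itself on the antagonist maximum. It does not: 10 days is the plan, 18 is the maximum, and 18 is repeated consistently.
- A reader might infer that the safety basis is contradicted. The Risks section reports 16 days as experience and does not call it a limit. What remains is a gap in support.
- A reader might take the reference to pills as permission for 18 days of methyltestosterone, the only pill in Aims 1 to 3. That requires ignoring both the drug named in the sentence and the separate 11-day limit. The word is most likely a drafting slip.

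The case against material bias also has weight. The Background says suppression is reached after two days of antagonist, so women at 10 and at 18 days are both past that point. Assignment is random, extension is described as rare and driven by scheduling, and no reason is given for it to differ by arm. The statistical section compares antagonist with antagonist plus testosterone, but does not name a between-arm Day 10 contrast.

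Most of this stands, and it limits the size of the problem. It does not remove it. The two-day statement concerns hormone levels, not baroreflex, nerve-activity or renin-angiotensin outcomes, and the plan itself measures antagonist-only women at both Day 3 and Day 10. The limits also allow different maximum exposures in the two arms, whatever the cause of extension. The payment arithmetic is administrative and serves only as supporting evidence of unsettled durations.

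**Conclusion.** The point holds in three parts: the drug form conflicts with the rest of the plan; the antagonist-only arm has no applicable extended test day; and 18 antagonist days cannot be combined with the 11-day androgen limit while the antagonist-alone test stays at Day 3. The third part assumes a lead-in of 2 to 3 days and androgen given up to the final test, as the planned schedule has it.

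Only extended women are affected. Since the plan calls extension rare and gives no count, the effect on the results is probably small and cannot be quantified. The risk sentence and the payment ceilings are secondary: the first lacks support for the last 2 days, and the second shows that the durations were not carried through consistently.

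**What to change.** The investigator should reconcile these passages; this review does not choose any duration or schedule.

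- State the form of each drug once, consistently.
- Reconcile the two maximum durations with each other and with the fixed Day 3 test.
- Give an extended test-day rule that applies to both arms.
- Support the sentence that extension adds no risk, or restate it.
- Align the payment ceilings with whatever durations are allowed.
- Record each woman's actual days on antagonist and on methyltestosterone. Per-day payment implies some count of Antagon days, but the plan describes no dosing log and no such payment for testosterone.
- Report the final-visit comparison with all women, and again without extended women as a sensitivity analysis.

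The cost is protocol wording, two recorded day counts per woman and one small additional analysis. Sample size and visits do not change.
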